Revised Protocol 03	29-Oct-2017	This protocol was updated mainly to incorporate preliminary results of drug-drug interactions studies IM006-031 and IM006-032 as described in Dear Investigator Letter dated 17-Oct-2016. Revisions were also made to provide further clarifications on study timelines, leflunomide washout, inclusion and exclusion criteria, PI expectations on x-ray and MRI results, Physicians Global Assessment of Disease Activity (PGA) and Joint Count Assessments, as well as to include administrative changes.
Revised Protocol 02	04-Aug-2016	Incorporates Amendment 07
Amendment 07	04-Aug-2016	[REDACTED]
Administrative Letter 03	21-Jun-2016	Editorial revision to Table 5.1-1 Flow Chart for Protocol IM006016 - Screening Period, to align with Section 3.3.1 Inclusion Criteria 2e
Revised Protocol 01	03-May-2016	Incorporates Amendment 05
Amendment 05	03-May-2016	Incorporate changes in response to health authorities' comments and update information collected during course of study.
Administrative Letter 02	16-Dec-2016	Correct the typographical error in the packaging/appearance of the study drugs (BMS-986142, 50 mg and placebo) in Section 4 of the protocol.
Administrative Letter 01	13-Nov-2015	Clarify information on Additional Research Amendment that describes in details Optional Sampling.
Original Protocol	14-Sep-2015	Not Applicable

SYNOPSIS

Clinical Protocol IM006016

Protocol Title: Phase 2, Randomized, Multi-Center, Double-Blind, Dose-Ranging, Placebo Controlled, Adaptive Design Study to Evaluate the Efficacy and Safety/Pharmacokinetics of BMS-986142 in Subjects with Moderate to Severe Rheumatoid Arthritis with an Inadequate Response to Methotrexate with or without TNF Inhibitors

Investigational Product(s), Dose and Mode of Administration, Duration of Treatment with Investigational Product(s):

BMS-986142 is a reversible Bruton's tyrosine kinase (BTK) inhibitor that will be orally administered in a double-blind fashion to rheumatoid arthritis (RA) subjects currently on a background of methotrexate (MTX) treatment. Four treatments will be administered: placebo, 100, 200, and 350 mg of BMS-986142 daily for 12 weeks. Additionally, new dose levels of BMS-986142 may be added based on the results of Week 4 interim analysis.

Study Phase: 2

Research Hypothesis: At least one of the dose levels of BMS-986142 administered daily is more effective than placebo on a background of methotrexate (MTX) in achieving ACR20 and ACR70 response after 12 weeks of treatment in subjects with moderately-to severely active RA with an inadequate response to MTX with or without TNF inhibitors.

Primary Objective:

To compare the efficacy of BMS-986142 versus placebo (PBO) on a background of MTX as assessed by ACR20 and ACR70 response rates at Week 12.

Secondary Objectives:

- 1) Assess additional efficacy outcomes of BMS-986142 at Week 12 and over 12 weeks of treatment as measured by ACR20, ACR50 and ACR70 response rates, DAS28-CRP change from baseline, DAS28-ESR change from baseline, Clinical Disease Activity Index (CDAI), Simplified Disease Index (SDAI), and Boolean remission.
- 2) Assess the safety and tolerability of BMS-986142.
- 3) Evaluate pre-dose concentration (C_{trough}) of BMS-986142.
- 4) Assess the efficacy of BMS-986142+MTX to -MTX in reducing synovitis, osteitis, bone erosions, and cartilage loss in hands/wrists by MRI at Weeks 4, and 12 from baseline.

[REDACTED]

Study Design:

This is a 12 week randomized, double-blind (DB), placebo-controlled, dose-ranging study with adaptive design features based on an interim analysis. The study will initially have a Screening Period (with 2 screening visits for subjects that require DMARD washout) that will be followed by up to 12 weeks of DB treatment and then a follow-up period of 30 days. At the end of the DB study period, alternate treatments for RA should be discussed with subjects.

Ongoing assessment of safety will be performed by an independent Data Monitoring Committee (DMC).

Screening Period:

The standard duration of the Screening Period is up to 28 days, with two Screening Visits allowed for subjects who require washout. Should more time be needed, the duration of the Screening Period may be extended up to another week (total of five weeks) depending on current DMARDs washout, drug stabilization, MRI technical issues, and subject scheduling.

The start of the trial is defined as first visit for first subject screened. End of trial is defined as the last visit or scheduled procedure shown in the Time & Events schedule for the last subject. Study completion is defined as the final date on which data for the primary endpoint was or is expected to be collected, if this is not the same.

[figure not shown]
Study Summary: Subjects with moderate to severely active RA who have had an inadequate response to MTX with or without prior inadequate response to up to 2 TNF inhibitors will receive BMS-986142 or placebo daily for up to 12 weeks.

Upon meeting the Inclusion/Exclusion criteria, approximately 328 subjects will be randomized to 1 of the 4 treatment arms as shown in [Figure 1](#) below.

Interim analyses (IA) of clinical and PK data up to 12 weeks will be performed after approximately 20 subjects per treatment arm reach Week 4 (complete 4 weeks of treatment or discontinue) and complete the specified assessments for efficacy (ie, DAS28-CRP), safety, and PK. The purpose of this interim analysis is to adapt study design including dose, and sample size.

Subjects who were enrolled before the IA is completed will continue the originally assigned dose level if they have received at least 1 treatment and the dose is considered safe.

Figure 1: Study Design Schematic

Duration of Study:

Approximately 4 weeks for screening, 12 weeks of treatment, and 4 weeks of safety follow-up. Total duration for the study is approximately 20 weeks for the study and safety follow-up.

Number of Subjects:

About 328 subjects will need to be randomized for the 4 arms of this study. The study will utilize an equal randomization scheme that will result in approximately 82 subjects in each arm. Should the IA analysis for futility and dose adaptation suggest that an additional one or 2 dose levels be added, then up to 82 additional subjects per arm may be randomized for up to 408 total potential subjects and randomization ratio will be adjusted accordingly.

At this time, BMS (the Sponsor) has elected to stop recruitment to the study on November 30th 2017. The company regularly reviews its ongoing studies within development programs to determine acceptability of continuation due to changing business needs, benefit-risk and/or the desire to accelerate decisions to advance a program. The Sponsor want(s) to emphasize that the stopping of enrollment in this study, prior to recruiting the planned number of subjects is not related to any adverse events (AEs) associated with the use of BMS-986142.

Study Population:

Men or women (not nursing or pregnant) \geq 18 years of age with a diagnosis of RA by standard criteria at least 16 weeks prior to screening and who are inadequate responders to MTX with or without inadequate response to up to 2 TNF inhibitors.

Key Inclusion Criteria:

Note: Please see main protocol for complete listing of Inclusion/Exclusion criteria

1. Documented diagnosis of adult-onset RA as defined by standard criteria (ACR/EULAR [2010]) at least 16 weeks prior to screening.
2. ACR global functional status class of 1 to 3.
3. Subjects must be MTX inadequate responders based on investigator’s judgment. Subjects must have been taking MTX for at least 3 months at a minimal weekly dose of 15 mg, and at a stable dose for 4 weeks prior to

randomization (Day 1). A lower dose of MTX is permitted, if there is verifiable documentation in the medical record that the subject could not receive or reach a weekly dose of 15 mg due to toxicity or intolerance and the dose is at least 10 mg MTX at the time of screening. In Japan, Korea, Taiwan, Canada, and any other country that requires the same rule, a minimum dose of 7.5 mg per week is permitted.

NOTE: Subjects using parenteral MTX for administration of their weekly dose may be included.

To minimize potential of MTX toxicity, all subjects should receive folic acid, folinic acid, or leucovorin according to manufacturer recommendations and local medical standard of care guidelines.

4. Subject failed or was intolerant to ≤ 2 TNF inhibitor(s), (failed, defined as the inability to achieve desired efficacy at an approved labeled dose for at least 12 weeks as determined by the investigator). Target population includes at least 70% of patients that had inadequate response to MTX and up to 30% of patients in addition to inadequate response to MTX need to have failure or intolerance to up to 2 TNF inhibitors.
5. Minimum of 6 swollen and 6 tender joints on a 66/68 joint count on Screening Visit #1 for those not requiring washout and on Screening Visit #2 for those requiring DMARD washout.
6. Evidence of swelling in at least 1 joint of hand or wrist by clinical examination on Screening Visit #1 for those not requiring washout and on Screening Visit #2 for those requiring washout.
7. Subjects must have a hsCRP of ≥ 0.8 mg/dL (8mg/L) [by central laboratory values] or an ESR ≥ 28 mm/hr on Screening Visit #1 for those not requiring washout of DMARDs and on Screening Visit #2 for those requiring washout.
8. This study permits the re-enrollment of a subject that has discontinued the study as a pre-treatment failure (ie, subject has not been randomized / has not been treated). If re-enrolled, the subject must be re-consented and a new subject number obtained.

Study Drug: includes both Investigational [Medicinal] Products (IP/IMP) and Non-investigational [Medicinal] Products (Non-IP/Non-IMP) as listed:

Study Drug for BMS-986142		
Medication	Potency	IP/Non-IP
BMS-986142-01 Film Coated Tablet	50 mg	IP
Matching Film-Coated placebo for 50 mg BMS-986142-01 tablets	placebo	IP
BMS-986142-01 Film Coated Tablet	150 mg	IP
Matching Film Coated Placebo for 150 mg BMS-986142-01 tablets	placebo	IP
Methotrexate - background therapy subject taking on entry	See protocol Section 3.3.1 , Inclusion Criteria 2c for possible doses	Non-IP

Study Assessments:

Efficacy will be assessed using various RA endpoints including ACR 20/50/70 scores, CDAI, SDAI and Boolean remission rates, DAS28-CRP, DAS28-ESR and MRI. Physical function will be assessed via HAQ-DI. Safety (through reporting of adverse events, clinical laboratory results, physical examination, which includes vital signs and ECGs), population pharmacokinetics, and exposure-response relationships will also be assessed.

Statistical Considerations:

Sample Size:

The sample size calculation is driven by the power to compare the proportion of subjects who achieve ACR70 response at Week 12 between each BMS-986142 dose arm and placebo arm. The target population consists of mixed subjects who are MTX-IR ($\geq 70\%$) and TNF-IR ($\leq 30\%$). For co-primary endpoint of ACR70 at Week 12, 82 subjects per arm will provide $\sim 90\%$ power to detect a treatment difference of 17% at the type I error rate of $\alpha = 0.05$ (two-sided), assuming the placebo response rate of 2.5%. The assumed treatment difference of 17% is about double of median difference observed from historical data on approved drugs across different mechanism of actions (MOAs).

For the other co-primary endpoint of ACR20 at Week 12, 82 subjects per arm will provide $>99\%$ power to detect a difference of 34% over placebo at the type I error rate of $\alpha = 0.05$ (two-sided), assuming placebo response rate of 33%. The assumed treatment difference of 34% and placebo response rate of 33% were based on the observed data from approved drugs across different MOAs.

An interim analysis (IA) will be conducted when about 20 subjects per treatment arm reach week 4 (complete 4 weeks of treatment or discontinue). Based on the totality of efficacy, safety, and PK data at Week 4 IA, the following adaptation(s) may be recommended:

- Stop inefficacious or unsafe dose(s)
- Introduce new dose(s) arms if needed and enroll up to about 82 subjects per new arm
- Complete full enrolment for all efficacious arms (up to about 82 subjects per arm)
- Stop the study enrollment if all dose arms are stopped for safety or futility.

The total sample size (range from 328 to 408 subjects) varies depending on actual enrollment rate, number of dropped dose arm(s) and number of newly added dose arm(s). The details of interim analysis and the criteria to adapt dose arm(s) and stop for futility are specified in the [section 8.5](#).

Endpoints:

Co-Primary

- ACR20 response rate at Week 12
- ACR70 response rate at Week 12

Secondary

- Signs and Symptoms: ACR20/ACR50/70 over time
- Remission and change from baseline: DAS28-CRP, DAS-ESR, SDAI, CDAI, Boolean over time
- PK: Ctrough of BMS-986142
- Change in RAMRIS Scores of synovitis, osteitis, bone erosion and cartilage loss from baseline to Week 4 and Week 12

Statistical Analyses:

Efficacy analysis:

The co-primary endpoint ACR 20 and ACR70 response rate at Week 12 will be summarized for each treatment group using point estimate and 90% confidence intervals (CIs). Treatment difference of ACR 20/ACR70 response rate at Week 12 between each BMS-986142 arm versus placebo will be provided with point estimate and two-sided 95% CIs. The chi-square tests will be used to compare the ACR response rates at Week 12 between each of the active treatment arms and the placebo arm at type I error rate of 0.05. Within each treatment group, the statistical testing will be performed for ACR20 at level of 0.05 first. If it is statistically significant, then the statistical testing will be performed for ACR70. Otherwise, stop testing for this treatment group. All treatment groups will follow the

same testing procedure. All subjects who discontinue prematurely during the treatment period or receive rescue therapy will be counted as non-responder at subsequent visits.

Safety analysis:

All safety presentations will be based on the As-Treated population. Frequency distribution and individual listings of all adverse events, laboratory abnormalities and vital signs will be generated. Changes in clinical laboratory test results from baseline will be provided. No formal statistical tests on the treatment difference will be performed for any safety analyses.

Pharmacokinetic analysis:

Ctrough values will be descriptively summarized by treatment and study days.

[figure not shown]
[figure not shown]
[figure not shown]
[figure not shown]
[figure not shown]

[figure not shown]
[figure not shown]
[figure not shown]
[figure not shown]
[figure not shown]
[figure not shown]

[figure not shown]
[figure not shown]
Preliminary population PK and dose/exposure-response (ie, DAS28-CRP and selected safety endpoints) analysis will be conducted at the time when Week 4 interim analysis is conducted to assist new dose selection as described in interim analysis section (See [section 8.5](#)).

Once the study is completed, the concentration vs. time data from this study combined with PK data from additional studies will be used to further develop a population PK model. This model will be used to evaluate the effects of various covariates on the PK of BMS-986142. [REDACTED]

Week 4 Interim analysis (IA):

After about 20 subjects per treatment arm have completed at least 4 weeks of the treatment period or discontinued the treatment, an interim analysis will be conducted to assess the efficacy of the BMS-986142 dose arms and the overall safety. The interim analysis will use pre-specified efficacy, safety and PK endpoints. The results of the interim analysis will be reviewed by an unblinded sponsor team who is not involved in the study conduct and who will provide recommendations with regard to the adaptive design decisions to the blinded study team. The details of interim analysis and the criteria to adapt dose arm(s) and stop for futility are specified in the Section 8.5.

TABLE OF CONTENTS

TITLE PAGE	1
DOCUMENT HISTORY	3
	4
SUMMARY OF KEY CHANGES FOR REVISED PROTOCOL 03	4
SYNOPSIS.....	10
TABLE OF CONTENTS.....	16
1 	20
	20
	20
	21
	22
	25
1.2 Research Hypothesis.....	25
1.3 Objectives	26
1.3.1 Primary Objectives	26
1.3.2 Secondary Objectives.....	26
	26
	27
	27
	27
	31
	32
	34
1.5 Overall Risk/Benefit Assessment	36
2 ETHICAL CONSIDERATIONS.....	37
2.1 Good Clinical Practice	37
2.2 Institutional Review Board/Independent Ethics Committee.....	37
2.3 Informed Consent.....	38
3 INVESTIGATIONAL PLAN.....	39
3.1 Study Design and Duration.....	39
3.2 Post Study Access to Therapy.....	41
3.3 Study Population.....	42
3.3.1 Inclusion Criteria.....	42
3.3.2 Exclusion Criteria.....	45
3.3.3 Women of Childbearing Potential	49
3.3.4 MRI Contraindications	50
	50
	50
	51
3.4.2 Other Restrictions and Precautions.....	52
3.4.2.1 Immunizations	52
3.4.2.2 Infectious Complications	52

3.5 Discontinuation of Subjects following any Treatment with Study Drug.....	52
3.6 Post Study Drug Study Follow up	53

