For subjects who are no longer treated with leflunomide prior to screening for at least 10 weeks: Leflunomide plasma levels will be obtained at Screening; if the levels are non-detectable [less than 0.02 mg/L or 0.02 mcg/mL], the subject is eligible to enroll immediately if they have not been treated with leflunomide within 10 weeks prior to Screening. If there are still detectable leflunomide plasma levels, the subject may enroll only if they follow the above drug elimination procedure.

[figure not shown]
The standard duration of the Screening Period is up to 28 days, with two Screening Visits allowed for subjects who require washout.

Should more time be needed, the duration of the Screening Period may be extended up to another week (total of five weeks) depending on current DMARDs washout, drug stabilization, MRI technical issues, and subject scheduling.

Double-Blind Period:

Upon meeting the Inclusion/Exclusion criteria and completing the screening period, approximately 328 subjects will be randomized to 1 of the 4 treatment arms in an equal ratio as shown in the study schematic [Figure 3.1-1](#) below.

Figure 3.1-1: Study Design Schematic

During this period, the dose of methotrexate, NSAIDs, and oral prednisone (or its equivalent) should remain stable. Intra-articular corticosteroid injections and intramuscular injections are not permitted. Analgesics are permitted with certain restrictions (see [Section 3.3](#)).

At the end of the DB period, alternate therapies for RA should be discussed with subjects.

The start of the trial is defined as first visit for first subject screened. End of trial is defined as the last visit or scheduled procedure shown in the Time & Events schedule for the last subject. Study completion is defined as the final date on which data for the primary endpoint was or is expected to be collected, if this is not the same.

Interim Analyses:

Interim Analyses (IA) of clinical and PK data will be performed after approximately 20 subjects per treatment arm reach Week 4 (complete 4 weeks of treatment or discontinue) and complete the specified assessments for efficacy (ie, DAS28-CRP), safety, and PK. Details of interim analyses are described in [Section 8.5](#) (Interim analysis).

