8 STATISTICAL CONSIDERATIONS

8.1 Sample Size Determination

The sample size calculation is driven by the power to compare the proportion of subjects who achieve ACR70 response at Week 12 between each BMS-986142 dose arm and placebo arm. The target population consists of mixed subjects who are MTX-IR ($\geq 70\%$) and TNF-IR ($\leq 30\%$). For co-primary endpoint of ACR70 at Week 12, 82 subjects per arm will provide ~ 90% power to detect a treatment difference of 17% at the type I error rate of $\alpha = 0.05$ (two-sided), assuming the placebo response rate of 2.5%. The assumed treatment difference of 17% is about double of median difference observed from historical data on approved drugs across different mechanism of actions (MOAs).

If the placebo response rate in ACR70 at Week 12 is higher than planned 2.5% (eg, 5%), 82 subjects per arm can still provide 84% power to detect a difference of 17%.

For the population of MTX-IR ($\geq 70\%$), 57 subjects per arm will provide 78% power to detect a treatment difference of 18% in ACR70 at the Type 1 error rate of $\alpha = 0.05$ (two-sided), assuming the placebo response rate is 2.5%.

For the other co-primary endpoint of ACR20 at Week 12, 82 subjects per arm will provide >99% power to detect a difference of 34% over placebo at the type I error rate of $\alpha = 0.05$ (two-sided), assuming placebo response rate of 33%. The assumed treatment difference of 34% and

placebo response rate of 33% were based on the observed data from approved drugs across different MOAs.

For the population of MTX-IR ($\geq 70\%$), 57 subjects per arm will provide 95% power to detect a treatment difference of 35% in ACR20 at the Type 1 error rate of $\alpha = 0.05$ (two-sided), assuming the placebo response rate is 40%.

An interim analysis (IA) will be conducted when about 20 subjects reach week 4 (complete 4 weeks of treatment or discontinue). Based on the totality of efficacy, safety, and PK at Week 4 IA, the following adaptation(s) may be recommended:

- Stop ineffective or unsafe dose(s)
- Introduce new dose(s) arms if needed and enroll (up to about 82 subjects per arm)
- Complete full enrolment for all efficacious arms (up to about 82 subjects per arm)
- Stop the study enrollment if all dose arms are stopped for safety or futility;

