The total sample size varies depending on the interim analysis results (range from 328 to 408 subjects). The details of interim analysis and the criteria to adapt dose arm(s) and stop for futility are specified in the [Section 8.5](#).

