7.5 Efficacy

The efficacy analyses will be performed using the efficacy analysis population. The results will be grouped by “as randomized” treatment groups, unless otherwise specified. No formal statistical testing was pre-specified for other efficacy endpoints except the primary endpoint of ACR20 and ACR70 response at Day 85. The analyses of binary endpoints and continuous endpoints will be provided over time including the milestone visits (e.g. Day 85).

Note: If the enrollment is terminated for all treatment arms based on Week 4 interim analysis, the sensitivity analyses, per-protocol analyses, sub-group analyses and additional analyses as defined in the following sections may not be performed based on smaller sample size.

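### The protocol stops recruitment on a fixed date short of plan, but still presents 328 subjects, 82 per arm and ~90% ACR70 power as the trial's size

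*Protocol*

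**What the plan says.** Protocol synopsis, Number of Subjects, states that the sponsor "has elected to stop recruitment to the study on November 30th 2017". It describes this as "the stopping of enrollment in this study, prior to recruiting the planned number of subjects" and says it is unrelated to adverse events. The grounds given are general: business needs, benefit-risk, or a wish for faster decisions. The Week 4 interim is not named.

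The rest of the same version was not changed to match:

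- The paragraph just before the stop announcement: "About 328 subjects will need to be randomized for the 4 arms of this study". It gives about 82 per arm and up to 408 in total if doses are added.
- Protocol 3.1: "approximately 328 subjects will be randomized to 1 of the 4 treatment arms in an equal ratio".
- Protocol 8.1 and the synopsis: "82 subjects per arm will provide ~ 90% power to detect a treatment difference of 17" percentage points in ACR70 over a 2.5% placebo rate, with >99% power for ACR20 (33% plus 34 points).
- Protocol 8.1: "The total sample size varies depending on the interim analysis results (range from 328 to 408 subjects"). The option to open new arms remains here, in the synopsis and in 8.5.

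SAP section 5 (version 1.0, 12/04/2015) also rests on 82 per arm and a total of 328 to 408. SAP 7.5 lets certain analyses be dropped for a smaller sample, under one condition: "If the enrollment is terminated for all treatment arms based on Week 4 interim analysis".

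**The concern.** By the sponsor's own statement the total will fall short of plan, yet the lowest total that Protocol 8.1 allows for is the planned 328. Nothing gives the number randomized so far, the number expected, or the power at that number.

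ACR70 is where this matters. It drives the sample size, and within each dose it is tested only after ACR20 succeeds. A result with ACR20 significant and ACR70 not is quite possible in a smaller trial. Someone reading it against a printed ~90% power would take the ACR70 result as stronger negative evidence than it is.

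The SAP adds a smaller problem. Its reduced-enrolment note is tied to the interim analysis. It does not say whether the sensitivity, per-protocol, subgroup and additional analyses are kept when the sponsor ends enrolment for another reason. That choice should not be left until after unblinding.

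**Working it through.** **Inputs.** Protocol 8.1: ACR70 2.5% on placebo, difference 17 points (so 19.5% on active), 82 per arm, two-sided alpha 0.05. ACR20: 33% versus 67%. Test: chi-square, each active arm against placebo (Protocol 8.4.2, SAP 7.5.1). The final n per arm is not given, so a range is shown, assuming equal arms.

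**Formula.** Power = Φ[(d − c − 1.96·s0)/s1], where d is the difference, s0 = √(2·p̄(1−p̄)/n), s1 = √((p1(1−p1)+p2(1−p2))/n), and p̄ is the mean of the two rates. The continuity correction is c = 1/n; uncorrected, c = 0.

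**Reproducing the plan at n = 82.** p̄ = 0.11. s0 = √(0.1958/82) = 0.0489. s1 = √(0.18135/82) = 0.0470.

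- Corrected: (0.17 − 0.0122 − 0.0958)/0.0470 = 1.319, power 90.6%. The protocol states ~90%.
- Uncorrected: power 94.3%.

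The corrected form also matches the protocol's other figures: 84.8% for a 5% placebo rate (stated 84%), 78.5% for ACR70 at 57 per arm (78%), 99.1% for ACR20 (>99%) and 95.9% for ACR20 at 57 per arm (95%). The sponsor therefore appears to have sized the trial this way, although no formula is named.

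**Example at n = 60.** s0 = √(0.1958/60) = 0.0571, s1 = √(0.18135/60) = 0.0550.

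- Corrected: (0.17 − 0.0167 − 0.1120)/0.0550 = 0.752, power 77.4%.
- Uncorrected: (0.17 − 0.1120)/0.0550 = 1.055, power 85.4%.

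**Range.** The exact column sums binomial probabilities over all tables in which the uncorrected chi-square test rejects.

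| n per arm (total) | ACR70 corrected | ACR70 uncorrected | ACR70 exact chi-square | ACR20 corrected |
|---|---|---|---|---|
| 82 (328) | 90.6% | 94.3% | 96.8% | 99.1% |
| 70 (280) | 84.7% | 90.4% | 94.2% | 97.8% |
| 60 (240) | 77.4% | 85.4% | 90.2% | 95.4% |
| 50 (200) | 67.5% | 78.4% | 83.7% | 90.6% |
| 40 (160) | 54.7% | 68.7% | 77.2% | 81.9% |

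For 90% ACR70 power, 81 per arm are needed with the correction and 70 without. The ACR70 difference detectable with 90% power (corrected) is 16.8 points at 82 per arm, 21.2 at 60 and 28.9 at 40. Uncorrected, it is 18.9 at 60.

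**Dates.** Revised Protocol 03 is dated 29 October 2017, 32 days before the stop. Protocol 8.2 defines enrolled subjects as those who sign consent, and Table 5.1-1 places enrolment at Screening Visit 1. Screening may last up to five weeks. If recruitment is read as enrolment, a subject who consents on 30 November could be randomized as late as 4 January 2018 (35 days later).

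**The case against.** The power sentence is conditional: it says what 82 per arm would give, and it is right. The stop is disclosed directly after the 82-per-arm text, so nobody is misled about the fact of a shortfall. The planned test is a chi-square test with no correction mentioned, and run that way it keeps about 90% ACR70 power down to 60 per arm. ACR20, the other co-primary, is robust. The main analysis does not depend on 82 per arm: the tests, non-responder imputation and 95% confidence intervals for the treatment difference are already planned, so an imprecise ACR70 result would show as imprecise.

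All of that stands, and it limits the point. It does not remove the contradiction. The protocol gives a size and a total range that it also says will not be met, and supplies no replacement.

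Three stronger readings are tempting, and the documents do not support them:

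- *The stated power is false.* It is correct at 82 per arm. What has been superseded is the expectation of reaching 82.
- *The trial can no longer answer its primary objective.* The shortfall is not given. A small one costs little, and ACR20 power survives a large one.
- *No new arm can be filled, so the option is dead.* Thirty-two days against screening of up to 28 days, extendable to five weeks, makes a new start hard. But the documents do not say whether the interim has taken place or an arm has already been added. Protocol 8.5 sizes an added lower-dose arm at about 40, not 82.

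**Conclusion.** The point holds as a contradiction within the current protocol that needs reconciling. The planned size, the 328 to 408 range and the power tied to 82 per arm no longer describe the trial being run.

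The loss cannot be fixed from the documents. At 70 per arm, ACR70 power is between 84.7% and 94.2% depending on the calculation; at 40 it is between 54.7% and 77.2%. The corrected column is the like-for-like comparison with the sponsor's figures. The exact column is closer to the planned test if it is run without a correction. Both assume equal arms and the protocol's own response rates; an arm closed at the interim would change the picture.

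The SAP gap is narrow. It concerns which supporting analyses will be run, not the primary analysis. A version from 2015 could not have foreseen this stop.

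**What to change.** Before unblinding:

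1. In the synopsis, Protocol 3.1 and 8.1, and SAP section 5, replace the 328, 82-per-arm and 328 to 408 figures with the number expected from subjects enrolled (consented) by the stop date and later randomized. A count of those randomized by 30 November could miss subjects still in screening.
2. In the same places, restate ACR70 and ACR20 power and the detectable difference at that n per arm, and name the formula.
3. Reconcile the added-arm and 408-subject text with the stop. State whether the interim has taken place and whether any added arm exists. Do not simply delete the text, since it may be the authority for an arm already open.
4. Extend the SAP 7.5 note to a sponsor-decided stop, and list which sensitivity, per-protocol, subgroup and additional analyses will be run.

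The cost is wording in two documents and one recalculation. No further patients are needed. The stated power becomes less favourable.
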